5.2.11.3. Laboratory Measures – Chemistry/Hematology Panel

Continuous measures and their change from baseline to 24-week endpoint in the chemistry and hematology panels will be summarized using descriptive statistics at baseline and at 24-week endpoint for the FAS population.

In addition, continuous measures and their change from baseline to 24-week endpoint will be analyzed using the ANCOVA model with treatment, pre-study treatment (Lantus®-bolus, other basal-bolus, premixed insulin), and pre-study metformin or acarbose usage (metformin only, acarbose only, or neither) as fixed effects and the baseline value of HbA_{1c} level and the baseline of the response variable as covariates. The LSM means will be estimated using the observed margins (OM) option in SAS GLM procedure.

For each chemistry and hematology analyte, the number and percent of patients with treatment emergent high (within normal range at baseline, greater than the upper limit at Week 24/Early Discontinuation) and treatment emergent low (within normal range at baseline, less than the lower limit at Week 24/Early Discontinuation) will be presented and analyzed using Fisher's exact test or Pearson's chi-square test.

5.2.11.4. Laboratory Measures – Insulin Antibodies

At each visit (baseline, visits 4, 8, 11, and 24-week (last observation carried forward [LOCF])), total insulin antibody status (detected, not detected (ND), no test (NT)) will be collected. The lower limit of detection of total insulin antibodies is 0.26%. If antibodies are detected then the level of total percent binding will be recorded and cross reactive antibody status (detected, not detected (ND), no test (NT)) will be recorded. The lower limit of detection of cross-reactive antibodies is 1.06%. If cross-reactive antibodies are detected then the level of cross-reactive percent binding will be recorded.

Descriptive and inferential analyses will be performed for the set of FAS patients with a valid antibody testing (detected or ND) at baseline and at least one post baseline visit.

The proportion of patients with detected insulin antibodies will be summarized as counts and percentages at baseline, at each visit, at the 24-week endpoint (LOCF), and overall for the 24-week treatment period. At each of these time points, the proportion of patients with detected antibodies will be compared between treatment groups using Fisher's exact test. These analyses will be performed for patients with antibody levels detectable at baseline and for patients without detectable levels at baseline) in the FAS population.

In addition, the following listing will be provided for patients with detectable insulin antibodies at any time during the study: a listing of level of total insulin antibody percent binding across visits sorted by treatment and maximum postbaseline percent binding in descending order. Similar listings sorted by baseline percent binding as well as by endpoint percent binding will be provided. These listings will be provided for the FAS population.

The level of total insulin antibodies (expressed as percent binding) will be summarized by descriptive statistics (mean, median, SD, Q1, inter-quartile range (IQR), Q3, standard error, minimum, and maximum) at baseline, each visit, and endpoint (LOCF). At each of these time points, the median level of percent binding will be compared between treatment groups using the Wilcoxon rank sum test. Graphical displays of median percent binding and IQR at each visit and endpoint (LOCF) by treatment will be presented. These analyses will be performed for the FAS population, for patients with antibody levels detectable at baseline and without detectable levels at baseline.

All of the analyses above will be performed for the level of cross-reactive antibodies as well.

Categorical shift tables for total insulin antibodies with 4 categories (nondetectable, [0.26, 1.26), [1.26, 5), ≥ 5.0) of the level of insulin antibodies from baseline to endpoint (LOCF) and from baseline to maximum postbaseline value will also be presented.

Categorical shift tables for cross-reactive antibodies with 4 categories (nondetectable, [1.06, 2.06), [2.06, 5), ≥ 5.0) of the level of cross-reactive antibodies from baseline to endpoint (LOCF) and from baseline to maximum postbaseline value will also be presented.

The number and proportion of patients who have a treatment-emergent antibody response (TEAR) will be summarized by treatment at each post-baseline visit, at the 24-week endpoint (LOCF), and overall for the 24-week treatment period, then analyzed using Fisher's exact test or Pearson's chi-square test. Treatment-emergent AR is defined as an absolute increase of at least 1% in insulin antibody levels (measured in % binding) AND at least 30% relative increase from baseline [for patients who are insulin antibody-positive at baseline], or turning from insulin antibody-negative status at baseline to insulin antibody-positive during the course of the study with at least 1.26% binding (1% above the lower limit of detection) following treatment with study drug. The TEAR definition for patients who were antibody-negative at baseline takes into account the assay variability near the cut point of the assay (detectable antibody if $\geq 0.26\%$).

For patients with TEAR, a visit-wise listing of total and cross-reactive insulin antibody percent binding and clinical outcomes (HbA_{1c}, total hypoglycemia rate, basal insulin dose (U/Day, U/kg/Day), TEAE preferred terms) will be presented. The listing will be sorted by treatment and endpoint total insulin percent binding.

Incidence tables showing the number and percent of patients with initial and continuing TEAR at each visit will be presented. Similar analyses will be performed for the detection of total insulin antibodies and for the detection of cross reactive insulin antibodies.

Box plots of clinical outcomes (HbA_{1c}, total hypoglycemia rate, basal dose) will be generated by treatment and TEAR status.

In addition, the following patient listings of insulin antibodies (percent binding) will be provided for patients with TEAR: a listing of level of total insulin antibody percent binding across visit sorted by treatment and maximum postbaseline percent binding; a listing of level of total insulin antibody percent binding across visit sorted by treatment and endpoint percent binding. Similar listings will be presented for cross reactive percent binding.

In addition, the potential impact of total insulin antibody level and TEAR status on clinical response will be evaluated in several ways:

1. The relationship between the natural logarithm of the last observed insulin antibody levels (Ln[antibody level]) and selected clinical response variables (efficacy and safety measures (eg HbA_{1c}, total hypoglycemia rate, basal dose [U/day, U/kg/day], total dose [U/day, U/kg/day], premeal dose [U/day, U/kg/day]) will be evaluated using scatterplots and analyzed using ANCOVA on efficacy/safety measure as the dependent variable with treatment, pre-study treatment (Lantus®-bolus, other basal-bolus, premixed insulin), and pre-study metformin or acarbose usage (metformin only, acarbose only, or neither) as fixed effects; baseline HbA_{1c} level, Ln(antibody level) and treatment-by-Ln(antibody level) interaction as covariates for the FAS patients with detectable antibodies postbaseline and with valid antibody testing at baseline (detected, ND). A significant treatment-by-insulin antibody interaction may be indicative of a differential treatment effect necessitating further exploration to determine the nature of the interaction. Only patients with non-missing baseline value and at least one non-missing post-baseline value of the clinical response variable will be included in the analysis.
2. The relationship between TEAR and selected clinical response variables (efficacy and safety measures (e.g. HbA_{1c}, total hypoglycemia rate, basal dose [U/day, U/kg/day], total dose [U/day, U/kg/day], premeal dose [U/day, U/kg/day]) will be analyzed using ANCOVA on efficacy/safety measure as the dependent variable with treatment, TEAR (yes/no), pre-study treatment (Lantus®-bolus, other basal-bolus, premixed insulin), and pre-study metformin or acarbose usage (metformin only, acarbose only, or neither) , treatment-by-TEAR interaction as fixed effects and baseline HbA_{1c} level as a covariate for the FAS patients with detectable antibodies postbaseline and with valid antibody testing at baseline (detected, ND). A significant treatment-by-TEAR interaction may be indicative of a differential treatment effect necessitating further exploration to determine the nature of the interaction. Only patients with non-missing

baseline value and at least one non-missing post-baseline value of the clinical response variable will be included in the analysis.

3. The relationship between TEAR and overall incidence of categories of adverse events (TEAE, SAE, TEAE related to study drug, special topic allergic reactions, injection site reactions) will be assessed by showing the proportion of patients with an event for TEAR and non-TEAR patients by treatments for the FAS. For patients with and without TEAR, treatments will be compared using the Mantel-Haenszel test and the odds ratio and p-value from this test will be reported. The homogeneity of the odds ratios for TEAR and non-TEAR patients will be assessed using the Breslow-Day test.

The potential impact of cross-reactive antibody formation on clinical response similar to the analyses above will be done if there is sufficient number of patients with cross-reactive antibodies.

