5.2.8. Secondary Efficacy Outcomes and Methodology

The continuous secondary efficacy outcomes include:

- actual and change in HbA1c from baseline to 6, 12, and 18 weeks or LOCF
- 7-point SMBG measurements and change from baseline to each visit (expressed as plasma-equivalent glucose values), as listed in the Study Schedule (see ABES Study Protocol Attachment 1)
 - premeal for each meal
 - postmeal for breakfast and lunch
 - bedtime
 - 3 am
- summaries of 7-point SMBG (actual and change from baseline)
 - daily mean BG level (average across all 7 time points)
 - daily mean premeal BG level (before breakfast, lunch, dinner)
 - daily mean postprandial BG level (breakfast, lunch and bedtime)
 - bedtime to 3 AM excursion
- inpatient variability as measured by the SD of the 7-point SMBG.

- actual and change from baseline total insulin, basal insulin, and mealtime insulin lispro doses in U/day and U/kg/day
- actual and change from baseline in weight and BMI
- patient-reported outcomes as reflected in responses to ITSQ.

The analysis of the continuous secondary efficacy variables will be performed using the same MMRM model with treatment (LY2963016, Lantus®), pre-study treatment (Lantus®-bolus, other basal-bolus, premixed insulin), and pre-study metformin or acarbose usage (metformin only, acarbose only, or neither), visit, and interaction between visit and treatment as fixed effects; the baseline value of the response variable and the baseline HbA1c level as covariates; and a random effect for patient, with the FAS population.

The proportions of subjects achieving HbA1c target values (HbA1c <7.0% and ≤6.5%) at any point during the study (Weeks 6, 12, 18, 24, and 24-week endpoint [LOCF]) will be analyzed using Fisher's Exact test or Pearson's Chi-square test.

A listing of 7-point SMBG and 4-point SMBG will be presented for all the randomized subjects.

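### The antibody-impact ANCOVAs on insulin dose omit the baseline dose, which adds avoidable noise to the treatment-by-antibody interaction tests

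*SAP*

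**What the plan says.** SAP 5.2.11.4 evaluates the potential impact of antibodies on clinical response. The responses in items 1 and 2 are HbA1c, total hypoglycemia rate and the doses "basal dose [U/day, U/kg/day], total dose [U/day, U/kg/day], premeal dose [U/day, U/kg/day", which makes six dose outcomes. Each is "analyzed using ANCOVA on efficacy/safety measure as the dependent variable"; the SAP does not say whether that means the actual value or the change from baseline.

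Both models contain treatment, pre-study treatment class and metformin or acarbose use. Item 1 adds "baseline HbA_{1c} level, Ln(antibody level) and treatment-by-Ln(antibody level) interaction as covariates". Item 2 adds TEAR and has "treatment-by-TEAR interaction as fixed effects and baseline HbA_{1c} level as a covariate". In both, HbA1c is the only baseline measurement. Both close with the same inclusion rule: "Only patients with non-missing baseline value and at least one non-missing post-baseline value of the clinical response variable will be included in the analysis". A significant interaction with treatment is said to call for further exploration.

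Elsewhere the SAP does adjust for the baseline of the response. The MMRM in SAP 5.2.8, which covers these same dose variables, uses "the baseline value of the response variable and the baseline HbA1c level as covariates". The laboratory ANCOVA (5.2.11.3) and the vital-signs MMRM (5.2.11.5) do likewise. The general rule in SAP 5.2.1 names dose, but it describes the MMRM and yields where something else is noted, so it does not supply the term to an ANCOVA that is written out in full. Protocol Attachment 1 schedules the previous day's insulin dose at Visit 2.

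**The concern.** One covariate list serves every response. It suits HbA1c, where baseline HbA1c is the baseline of the response. It does not suit dose. The protocol derives the starting study dose from the prestudy dose (Protocol 9.1 and Attachment 5) and then adjusts it in steps, so baseline dose should be prognostic for on-study dose.

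Two things follow from leaving it out. First, variation that baseline dose would explain stays in the residual, which widens the standard error of the treatment-by-Ln(antibody) and treatment-by-TEAR terms. Those terms ask whether antibodies affect insulin requirement differently under LY2963016, so a real difference is easier to miss. Second, antibody level and TEAR are not randomised. If patients who needed more insulin before the study also carry more antibody, the antibody main slope will partly reflect that earlier difference.

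**Working it through.** **Plan's own figure.** The documents give no power, SD, correlation or antibody-positive count for these ANCOVAs. The only power figure is the study sample size, used here only as a reference N: 2 × (1.96 + 0.8416)² × 1.05² / 0.40² = 108.2, so 109 completers per arm (218 total). It reproduces.

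**Inputs.** Two-sided 5% for interaction tests (SAP 5.2.1). The correlation ρ between baseline and on-study dose, after the other model terms, is an assumption; the range shown is 0.5 to 0.8.

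**Interaction test.** Scale dose to unit variance at both times.

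- Residual variance with baseline dose in the model: 1 − ρ², whether actual dose or change is analysed.
- Without it: 1 for actual dose; 2(1 − ρ) for change.
- SE ratio, adjusted to unadjusted: √(1 − ρ²) for actual dose; √[(1 − ρ²)/(2(1 − ρ))] = √[(1 + ρ)/2] for change.
- An effect with 50% power as written has a standardised size of 1.96. Adjusted power = Φ(1.96/ratio − 1.96).

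| ρ | SE ratio, actual dose | Power, actual dose | SE ratio, change | Power, change |
|---|---|---|---|---|
| 0.5 | 0.87 | 62% | 0.87 | 62% |
| 0.7 | 0.71 | 78% | 0.92 | 57% |
| 0.8 | 0.60 | 90% | 0.95 | 54% |

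Example at ρ = 0.7, actual dose: 1.96/0.714 − 1.96 = 0.785, and Φ(0.785) = 78%.

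**Check by simulation** (3,000 runs per setting, N = 218, no correlation between Ln(antibody) and baseline dose, effect set so that the adjusted test has about 80% power). Power for actual dose without and with baseline dose: 67% and 79% at ρ = 0.5; 50% and 79% at 0.7; 24% and 78% at 0.9. An unadjusted change score gave 67%, 72% and 76%. The formula and the simulation agree.

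**Bias of the interaction.** Let g be the correlation of Ln(antibody) with baseline dose. With no true antibody effect given baseline dose, the unadjusted slope in each arm is ρg for actual dose, or −g(1 − ρ) for change. If g and ρ are the same in both arms, these cancel in the interaction. What remains is lost precision.

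**Main slope.** It does not cancel there. At ρ = 0.7 and g = 0.2, both assumed, it is 0.7 × 0.2 = 0.14 SD of dose per SD of Ln(antibody) for actual dose, and −0.2 × 0.3 = −0.06 for change. At g = 0 it is zero.

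**The case against.** A reader might infer that the antibody-dose slope in these models is spurious. Under assumed values (110 patients with detectable antibodies, g = 0.2, no true antibody effect), simulation gives false-positive rates of 16%, 32% and 37% at ρ = 0.5, 0.7 and 0.8 for actual dose, 18%, 12% and 9% for change, and about 5% with baseline dose included. The documents do not support that as a finding. They give neither correlation, and the figures presume that antibodies had no effect on the prestudy dose.

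The opposite direction is also possible. Item 1 uses the last observed antibody level, and the SAP expects some patients to be antibody-positive at baseline. If existing antibodies already raised insulin need, baseline dose carries part of that effect and adjustment removes it. With an assumed true slope of 0.2 SD at both times, a baseline-to-endpoint antibody correlation of 0.8 and 110 patients, the adjusted slope falls to 0.12, 0.09 or 0.07 at ρ = 0.5, 0.7 or 0.8, and power for the main slope falls from about 53–54% to 30%, 25% or 24%. This stands for item 1. It is weaker for item 2, because TEAR is defined by change from baseline. It does not reach the interaction in the same way: baseline dose precedes study drug, so adjusting for it cannot absorb a differential on-study effect.

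Three further points stand. The dependent variable is unnamed; if change was meant, the inclusion rule has an evident purpose and the power gain is smaller. Patients on premixed insulin have no separate basal and premeal dose before the investigator splits the total, so ρ may be lower for four of the six outcomes; SAP 5.2.8 has the same difficulty. And these are supportive analyses, shown beside scatterplots, box plots and listings, without multiplicity adjustment.

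None of this is a reason to omit a collected baseline value that the SAP uses for the same variables elsewhere.

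**Conclusion.** The point holds as one of precision and consistency. Items 1 and 2 require a baseline dose and then do not use it, against the SAP's own practice for these variables. The size depends on a correlation the documents do not state. Over 0.5 to 0.8, an interaction test at 50% power would gain 12 to 40 percentage points if actual dose is analysed, and 12 down to 4 if change is analysed. At a correlation near zero there is no gain on the actual-dose reading.

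The interaction is not shown to be biased; that would need confounding that differs between arms. Contamination of the main slope by prestudy insulin need is a possibility of unknown size and direction, not a demonstrated error. The primary HbA1c comparison and the gated secondary comparison are untouched.

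**What to change.** In SAP 5.2.11.4, items 1 and 2:

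- State whether the dependent variable is the actual value or the change from baseline.
- For the dose outcomes, add the baseline value of the response variable as a covariate and keep baseline HbA1c, matching SAP 5.2.8.
- In item 1, report the antibody main slope without baseline dose as well. State that, for patients antibody-positive at baseline, the adjusted slope describes on-study dose given baseline dose and may absorb an earlier antibody effect on prestudy dose.

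The cost is a short SAP edit, one model term per dose outcome and one extra reported slope. No patient is lost, because the inclusion rule already requires the baseline value. No new data are needed.

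### SAP 5.2.11.4 item 2 limits the TEAR yes/no ANCOVA to patients with detectable post-baseline antibodies, which removes only non-TEAR patients and changes the comparator

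*SAP*

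**What the plan says.** SAP 5.2.11.4 first sets a general population for the antibody analyses: "Descriptive and inferential analyses will be performed for the set of FAS patients with a valid antibody testing (detected or ND) at baseline" and at one or more later visits. Patients with no detectable antibody belong to that set.

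TEAR is then defined in two ways. For patients positive at baseline it is "an absolute increase of at least 1% in insulin antibody levels (measured in % binding) AND at least 30% relative increase from baseline". For the others it is "turning from insulin antibody-negative status at baseline to insulin antibody-positive during the course of the study with at least 1.26% binding". On the assay, the section states "The lower limit of detection of total insulin antibodies is 0.26" percent binding.

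The effect of antibodies on clinical response is examined in three numbered items:

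- **Item 1** is an ANCOVA with "Ln(antibody level) and treatment-by-Ln(antibody level) interaction as covariates".
- **Item 2** is an ANCOVA "with treatment, TEAR (yes/no), pre-study treatment" and prestudy metformin or acarbose use, with a treatment-by-TEAR interaction and baseline HbA1c.
- **Item 3** covers adverse events by "showing the proportion of patients with an event for TEAR and non-TEAR patients by treatments for the FAS".

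Items 1 and 2 carry the same restriction: "for the FAS patients with detectable antibodies postbaseline and with valid antibody testing at baseline". Item 3 does not. Nor do the box plots of HbA1c, total hypoglycemia rate and basal dose by treatment and TEAR status, planned earlier in the section.

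**The concern.** In item 1 the restriction has an evident purpose: the log of the antibody level needs a measured level. In item 2 the factor is binary, and a patient with valid tests and no detectable antibody has a clear value, namely no TEAR. The SAP gives no reason for the restriction there. The identical wording suggests that it was carried over from item 1, though that is an inference.

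Two things are at stake. The first is the question answered. The stated aim is to evaluate how TEAR status affects clinical response, but the restricted model compares TEAR patients only with patients who had some detectable antibody without a qualifying rise. The clearest non-responders are left out. Among baseline-negative non-TEAR patients, only those with a reading from 0.26% up to just under 1.26% stay in. The SAP says that the higher TEAR threshold for baseline-negative patients allows for assay variability near the cut point, so membership of the comparator partly rests on readings in that zone.

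The second is precision. Item 2 is the only planned model that tests treatment-by-TEAR on HbA1c, hypoglycemia rate and dose, and anti-glargine antibodies are part of a secondary safety objective (SAP 4.2).

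**Working it through.** **Which patients the restriction removes.** This step needs no assumed rates. Detectable post-baseline is read as detectable at any post-baseline visit.

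- Baseline-negative TEAR patient: binding of at least 1.26% by definition.
- Baseline-positive TEAR patient: baseline of at least 0.26% plus a rise of at least 1%, so at least 0.26 + 1.00 = 1.26%.
- Detection limit: 0.26%.

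Every TEAR patient is therefore detectable post-baseline, and the restriction removes none of them. Those removed are all non-TEAR: patients negative throughout, and patients positive at baseline but undetectable at every later visit.

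**What share of the non-TEAR group goes.** Let p be the share of tested patients with any detectable post-baseline antibody and t the TEAR share (t < p).

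- Non-TEAR, all: N(1 − t)
- Non-TEAR, kept: N(p − t)
- Share removed: (1 − p)/(1 − t)

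The share removed exceeds one half only if p < (1 + t)/2, that is p < 55% at t = 10% and p < 60% at t = 20%.

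**What it costs in precision.** For a simple TEAR versus non-TEAR contrast with a common SD, SE = SD × √(1/n_TEAR + 1/n_nonTEAR). The ratio of restricted to full SE is

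√{[1/t + 1/(p − t)] / [1/t + 1/(1 − t)]} = √[p(1 − t)/(p − t)].

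N and the SD cancel. If each TEAR group splits evenly between arms, the variance of the treatment-by-TEAR interaction is 4 × SD² × (1/n_TEAR + 1/n_nonTEAR), so the same ratio applies.

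**Inputs for the illustration.** The documents give no expected detection or TEAR rate, so there is no planned figure to reproduce; p and t are assumptions. N = 258 is the planned number randomized in SAP 5.1.1 (109/0.85 = 128.2, rounded up to 129 per arm).

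| p | t | TEAR | Non-TEAR, all | Non-TEAR, kept | Share removed | SE ratio |
|---|---|---|---|---|---|---|
| 30% | 10% | 26 | 232 | 52 | 77.8% | 1.16 |
| 30% | 20% | 52 | 206 | 26 | 87.5% | 1.55 |
| 50% | 10% | 26 | 232 | 103 | 55.6% | 1.06 |
| 50% | 20% | 52 | 206 | 77 | 62.5% | 1.15 |
| 80% | 10% | 26 | 232 | 181 | 22.2% | 1.01 |
| 80% | 20% | 52 | 206 | 155 | 25.0% | 1.03 |

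For p = 30%, t = 20%: √(0.30 × 0.80/0.10) = √2.4 = 1.55. For p = 50%, t = 10%: √(0.50 × 0.90/0.40) = √1.125 = 1.06. For p = 80%, t = 10%: √(0.80 × 0.90/0.70) = √1.029 = 1.01. On the planning SD of 1.05% for HbA1c change, the p = 30%, t = 20% case moves the SE from 0.163 to 0.253.

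**The case against.** The best defense is that this is one of several supportive explorations. A significant interaction only prompts further exploration, and the antibody and TEAR incidence comparisons are untouched. The restricted contrast is also a legitimate, narrower question: among antibody-positive patients, does a qualifying rise matter? And because TEAR is itself a post-baseline variable, any version of item 2 yields an association, not a causal effect. All of this stands. It limits the weight of the point, but it does not explain why item 2 uses a different comparator from item 3 and the box plots.

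Three stronger readings are tempting, and the documents do not support them.

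- A reader might infer that most of the non-TEAR comparator is lost. That holds only when p is below (1 + t)/2. Patients enter after at least 90 days on insulin (Protocol 8.1) and the detection limit is low, so a high detection rate cannot be ruled out.
- A reader might see a contradiction with the section's general antibody population. That population is broader, and an analysis may name a subset of it. The mismatch is with item 3 and the box plots.
- A reader might conclude that antibody-negative patients drop out of the TEAR assessment altogether. They are missing only from the item 2 ANCOVA.

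**Conclusion.** The restriction in item 2 serves no stated purpose, falls entirely on the non-TEAR group, and leaves a comparator that differs from the one used for TEAR elsewhere in the section. That follows from the SAP's definitions alone.

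The numerical effect rests on assumed rates. Within p of 30–50% and t of 10–20% the SE of the TEAR contrast rises by 6% to 55%; at high detection the loss of precision is negligible, and the narrower comparator is the remaining issue. The ratios assume equal residual SD in both sets and ignore covariate adjustment. The sample size and the primary noninferiority test are not affected.

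**What to change.** In item 2, define the population as FAS patients with a valid antibody result (detected or not detected) at baseline and at one or more later visits, and count those with no detectable antibody as non-TEAR. Keep the detectability restriction in item 1 only. If the narrower comparison is wanted, keep it as a labeled sensitivity analysis with its reason stated. Make the same check where the SAP extends these analyses to cross-reactive antibodies.

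The cost is one clause in the SAP and one filter in the program, on data already collected. It is best done before results by treatment are seen.
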